7.5 Efficacy

The primary and secondary efficacy analyses below will be performed using the IIT analysis population by as randomized treatment group. The primary analysis will be repeated using the PP analysis population. All other efficacy analyses will be performed using the ITT analysis population, unless otherwise specified.

For all time to event analyses, unless otherwise stated, subjects who do not achieve an efficacy endpoint (e.g., response) will be censored at the time of last non-missing visit in the double-blind period.

7.5.1 Hierarchical Testing for Primary and Key Secondary Endpoints

If the test for the primary endpoint (proportion of subjects who achieved IMACS DOI at Day 169) is statistically significant at a level of 5%, then a hierarchical approach for statistical testing will be used for the secondary endpoints. Hierarchical ordering of the secondary endpoints is as follows:

- Mean change from baseline in HAQ-DI at Day 169.
- MRC total improvement score at Day 169.
- Mean change from baseline in muscle endurance using FI-2 at Day 169.
- Mean change from baseline in MDAAT, based on the extramuscular disease activity VAS, at Day 169.

P-values will be presented for each of these endpoints. However, endpoints should not be interpreted for significance if they have a rank lower than that endpoint whose null hypothesis was the first that could not be rejected. That is, the significance of endpoints should not be interpreted if they have a rank lower than that endpoint whose test was the first to be non-statistically significant (p-value > 0.05).

7.5.2 Primary Efficacy Analysis

The primary comparison of proportion of subjects in IMACS DOI at Week 24 between the SC abatacept and placebo groups will be assessed using a logistic regression model. To account for randomization stratification, the logistic regression model will adjust for the randomization stratification variables of disease diagnosis (DM vs. Non-DM), Interstitial Lung disease status (present vs. absent), and Japan vs. ROW; baseline MMT8 score, baseline MDAAT, baseline PGA and treatment group will also be included in the model. Point estimates of the adjusted Odds Ratios (OR) of the odds of achieving IMACS DOI in the abatacept group compared to the placebo group, corresponding 95% CI and p-value will be provided. Point estimates of the proportion of subjects in IMACS DOI in each treatment group and corresponding 95% CI will also be provided. All subjects who discontinue study medication prematurely prior to reaching the Week 24 assessment visit and/or received rescued medication at any time during the 24 week double-blind period, will be considered as not achieving IMACS DOI for the primary analysis. Efficacy assessments collected at Week 24 on subjects who discontinue study medication prior to Week 24 will not be included in the primary analysis of the primary endpoint, but will be included in a sensitivity analysis of the primary endpoint. Details of imputation rules for classification of IMACS DOI response for subjects with missing components of IMACS are provided in [Section 8.1.9](#). A table summarizing the number of imputed values for the primary endpoint by treatment group and missing data pattern will be provided. A summary of number of missing IMACS core measure item by treatment group will also be provided for subjects whose IMACS data are missing at Week 24 because of missing component data.

The primary estimand of the treatment difference in the proportion of subjects with IMACS DOI at Day 169 is the odds ratio (abatacept versus placebo) in the ITT analysis population that would be observed if all subjects who prematurely discontinued or received rescue medication before Day 169 or had missing IMACS DOI data would be non-responders.

7.5.3 Sensitivity Analyses on the Primary Endpoint

7.5.3.1 Assess Impact of Rescue Medication

Sensitivity analyses of the primary endpoint will be performed based on the following scenarios:

- All subjects who meet criteria for disease worsening will be imputed as non-responders (i.e. not meeting IMACS DOI) whether they used rescue medication or not.
- All subjects who received rescue medication but continued in the double-blind period to Day 169 will be assessed for IMACS DOI based on their disease assessment on Day 169.

These sensitivity analyses will help assess the impact of the use of rescue medication on the primary endpoint.

7.5.3.2 Tipping Point Analyses

The robustness of the results of the primary endpoint will be assessed by varying the assumption of the missing data at the Week 24 (Day 169) based on the tipping point approach. This analysis will challenge the assumption that the effect of abatacept and placebo is the same for missing data by varying the percentage of missing considered as non-responders in both the abatacept and the placebo treatment group.

The missing data will be imputed using multiple imputation assuming the data are MNAR. The multiple imputation will utilize a logistic regression model that includes treatment group, age, gender, stratification variables of disease diagnosis (DM vs. Non-DM), Interstitial Lung disease status (present vs. absent), and Japan vs. ROW; baseline PGA score, baseline MMT-8 score and baseline MDAAT. The imputation will consider various scenarios including where dropouts on abatacept have lower response rate than dropouts on placebo. A series of analyses will be performed varying the distribution of responses among the missing data in each treatment group until the analysis conclusion of a statistically significant treatment effect no longer holds. The combination of number of responses among the missing data in each treatment group that overturns the primary results will represent a tipping point. An interpretation of clinical plausibility of the assumption underlying the tipping point will be provided.

Imputed data will consist of 100 imputed datasets; for each imputed dataset the missing IMACS DOI response will be imputed using the LOGISITIC method with a random seed number of 123611. Each of the imputed datasets will be analyzed using a similar logistic regression model used for the primary endpoint to get the estimate of odds ratio and 95% CI. Results from the analyses of each imputed datasets ORs and corresponding 95% CI will be combined using Rubin's imputation rules (using SAS MIANALYZE procedure) to produce the pooled estimate of OR and corresponding 95%, a pooled p-value for the test of null hypothesis of no treatment effect (i.e. OR = 1).

Analyses will be conducted by varying the log odds of achieving an IMACS DOI response (i.e. LOGIT of the probability of IMACS DOI response) among the missing data within each treatment arm. Resulting p-values will be displayed in a matrix that presents a range of logits corresponding to varying probabilities of response for missing values in both treatment arms; starting with a logit corresponding to a probability of response = 0.14 (this assumes 1 response out of 7 missing data) with increments of 0.3 on the logit until the logit is reached corresponding to a probability of response of .86 (this assumes 6 responses out of 7 missing data). The tipping point can then be identified (i.e. where a statistically significant treatment effect no longer holds). The adjustment in the logit function will be specified using the statement MNAR ADJUST available in SAS 9.3 or higher.

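### The tipping-point matrix is labelled by response probability but built by adjusting a model logit that contains treatment, and no rule links label to shift

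*SAP*

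**What the plan says.** SAP 7.5.3.2 (Tipping Point Analyses) describes the analysis in two ways.

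- **As absolute response rates among the missing.** "Resulting p-values will be displayed in a matrix that presents a range of logits corresponding to varying probabilities of response for missing values" in both arms. The grid is described as "starting with a logit corresponding to a probability of response = 0.14", explained as 1 responder among 7 missing, "with increments of 0.3 on the logit until the logit is reached corresponding to a probability of response of .86", explained as 6 of 7. The result is read on the same scale: "The combination of number of responses among the missing data in each treatment group that overturns the primary results will represent a tipping point". The SAP adds: "An interpretation of clinical plausibility of the assumption underlying the tipping point will be provided".
- **As an adjustment to a fitted model.** "The multiple imputation will utilize a logistic regression model that includes treatment group, age, gender, stratification variables of disease diagnosis", together with ILD status, region and baseline PGA, MMT-8 and MDAAT. The tool is then named: "The adjustment in the logit function will be specified using the statement MNAR ADJUST available in SAS 9.3 or higher".

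The section gives neither the shift values nor a formula that derives them from the target probabilities. It does promise scenarios in which abatacept dropouts respond less often than placebo dropouts.

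**The concern.** A response probability among the missing is an absolute quantity. An adjustment to a modelled logit is relative to what the model already predicts for that subject. The two coincide only when the modelled probability is 0.50, where the logit is zero. Because treatment is in the imputation model, the predicted logits normally differ between arms before any adjustment, so one shift applied to both arms leaves them apart.

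Clinical plausibility is to be judged at the tipping point. If a cell labelled with equal rates actually imputes a higher rate on abatacept, the reader judges a scenario that was not run. The same text also permits two programs, one that enters the grid logits as shifts and one that calibrates the shift per arm, and their p-values would differ.

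**Working it through.** **Inputs**
- Grid: 1/7 to 6/7 in logit steps of 0.3 (SAP 7.5.3.2).
- Stand-ins for the modelled response rates: 60% abatacept, 33% placebo (SAP section 5). The actual modelled rates are unknown.
- Assumption: the adjustment adds a constant to the modelled logit. This follows the SAP's own description of the tool.

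**The plan's grid.** logit(1/7) = −1.792 and logit(6/7) = +1.792. The span is 3.584, and 3.584 / 0.3 = 11.9, so about 12 steps, 13 values per arm and 13 × 13 = 169 cells. The grid reproduces and is symmetric about zero.

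**Imputed rate if the labelled logit is entered as the shift.** Rate = expit(logit(modelled rate) + logit(label)), with logit(0.60) = 0.405 and logit(0.33) = −0.708.

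| Label, both arms | Shift | Abatacept | Placebo | Difference |
|---|---|---|---|---|
| 0.14 (1/7) | −1.79 | 0.200 | 0.076 | 12.4 points |
| 0.50 | 0 | 0.600 | 0.330 | 27.0 points |
| 0.86 (6/7) | +1.79 | 0.900 | 0.747 | 15.3 points |

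Every equal-label cell keeps the modelled log odds ratio of 0.405 + 0.708 = 1.11. The 0.50/0.50 cell has zero shift, so it is plain missing-at-random imputation. Per 7 missing, the gap is 7 × 0.124 = 0.9 to 7 × 0.27 = 1.9 responders. The corner labelled 0.14 (abatacept) against 0.86 (placebo) imputes 0.20 against 0.75.

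**Other modelled rates.** The equal-label gap is 9 to 26 points at 50%/25%, 15 to 35 points at 60%/25%, and 2 to 5 points at an assumed weak effect of 40%/35%. With no modelled treatment effect it is zero.

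**Shifts that would make the labels true.** Shift = target logit − the arm's modelled logit.
- Label 0.14: −1.792 − 0.405 = −2.20 (abatacept); −1.792 + 0.708 = −1.08 (placebo).
- Label 0.86: +1.39 (abatacept); +2.50 (placebo).

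**Effect on p-values.** Assumed data, treatment-only imputation, unadjusted log odds ratio pooled by Rubin's rules. Values are simulated, so counts can move by a few cells.

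| Missing per arm | Observed responders | Result | Direct shift | Labels true |
|---|---|---|---|---|
| 7 | 37/68 vs 24/68 | significant cells of 169 | about 126 | about 102 |
| 7 | 41/68 vs 25/68 | significant cells of 169 | 166 | about 154 |
| 7 | 45/68 vs 25/68 | significant cells of 169 | 169 | 169 |
| 7 | 40/68 vs 27/68 | p at 0.50/0.50 | 0.027 | 0.043 |
| 7 | 41/68 vs 22/68 | p at 0.50/0.50 | 0.0012 | 0.0034 |
| 15 | 36/60 vs 20/60 | p at 0.50/0.50 | 0.003 | 0.018 |
| 15 | 35/60 vs 23/60 | p at 0.50/0.50 | 0.029 | 0.075 |

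Only the last row changes its conclusion on the diagonal. Its non-responder result is already borderline, at p = 0.045. In the first two rows the direct shift moves the boundary between significant and non-significant cells.

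**The case against.** The strongest reply is that the SAP never says the grid logit is the shift. It says the log odds of response among the missing will be varied within each arm, which describes a target. A programmer who calibrates the shift per arm would satisfy that text and produce correct labels on average. This stands: the mislabelling is conditional on the implementation and on a positive fitted treatment effect. The symmetric grid through zero does not settle the matter, because it fits direct shifts and absolute logits equally well.

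Three further points stand. The output is a two-way matrix, and its off-diagonal cells remain adverse to abatacept even under direct shift. Robustness does not rest on this grid alone: the primary analysis counts discontinued and missing subjects as non-responders (SAP 7.5.2), and SAP 7.5.3.3 uses Day 169 data collected after discontinuation. Near the planned effect with 7 missing per arm, no diagonal conclusion changed in the cases tried.

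What does not stand is that this is only omitted detail. The tipping point is defined in responder counts and the tool works on a relative scale, so the missing conversion rule decides where the tipping point falls.

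A reader might infer that the matrix is certain to favour abatacept, or that the primary result will look more robust than it is. The documents do not support that. The shift values are unstated, adverse scenarios are planned, and the size depends on the fitted effect and the amount of missing data.

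**Conclusion.** The concern holds in conditional form. SAP 7.5.3.2 presents the matrix by absolute response probability, implements it as an adjustment to a logit containing treatment, and does not connect the two. If the labelled logits are used as shifts, equal-label cells favour abatacept by 12 to 27 points at assumed modelled rates of 60%/33%, and the harshest scenario is milder than its label. The gap shrinks with a weaker modelled effect. It matters mainly when the result is borderline or more data are missing. This is a minor point that should be corrected; the primary analysis is unaffected.

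**What to change.** Choose one of the following and write it into SAP 7.5.3.2.

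1. Keep MNAR ADJUST, label both axes as log-odds shifts, and print in every cell the mean realised imputed response rate and responder count for each arm. Judge the plausibility of the tipping point on those realised values.
2. Keep the probability labels and state an arm-specific shift: target logit minus the arm's modelled logit. Because covariates spread the modelled logits within an arm, this holds only on average, so check the realised mean rate against the label.

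Enumerating k responders among the m missing in each arm is a simple supplement that matches the SAP's definition of the tipping point. Its drawback is that it ignores the imputation covariates.

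The cost is a few sentences in the SAP and a small programming change. No new data are needed.

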7.5.3.3 Sensitivity Analyses Based on Day 169 Data Collected after Discontinuation from Study

Subjects who discontinued the study prior to the Week 24 (Day 169) assessment are required by protocol to return for their Week 24 study visit similar to subjects continuing in the study; in

addition to the tipping point analysis above, the data collected on the discontinued subjects who did not receive rescue medication will be used to perform an additional sensitivity analysis of the primary endpoint. A similar model used for the primary analysis will be used; the logistic regression model will include randomization stratification variables of disease diagnosis (DM vs. Non-DM), Interstitial Lung disease status (present vs. absent), and Japan vs. ROW; baseline MMT-8 score, baseline MDAAT, baseline PGA and treatment group. Point estimate of the adjusted Odds Ratios (OR) of the odds of achieving IMACS DOI in the abatacept group compared to the placebo group, corresponding 95% CI will be provided, however no p-value will be calculated. Unadjusted point estimate of the proportion of subjects in IMACS DOI in each treatment group and corresponding 95% CI will also be provided. Subjects with missing Week 24 assessment will be considered non-responders in this sensitivity analysis.

7.5.4 Secondary Efficacy Analysis

In addition to the primary efficacy endpoint, analyses related to the secondary [REDACTED] [REDACTED] will also be included in the Week 24 analysis. The secondary efficacy assessment of change from baseline in muscle endurance using FI-2 up to Day 169 (Week 24) will be assessed using a longitudinal (repeated measures) model including treatment group, baseline FI-2 value and randomization stratification factors: diagnosis (DM vs. Non-DM), ILD, Japan vs. ROW, time (categorical as study visit at which FI-2 is measured), time by baseline FI-2 and time by treatment interactions as fixed effects and subject as a random effect. Adjusted mean, SE, 95% CI for adjusted mean difference between treatment groups by study visit will be provided.

A similar longitudinal model will also be used to assess the change from baseline in HAQ-DI up to Day 169 (Week 24). The model will include treatment group, baseline value HAQ-DI value, randomization stratification factors: disease diagnosis (DM vs. Non-DM), ILD, Region (Japan vs. ROW), time (categorical as study visit at which HAQ-DI is measured), time by baseline HAQ-DI and time by treatment interactions as fixed effects and subject as a random effect. Adjusted mean, SE, 95% CI for adjusted mean difference between treatment group by study visit will also be provided.

The secondary efficacy assessment of change from baseline in extra-muscular disease activity MDAAT value will also be assessed using a longitudinal (repeated measures) model including treatment group, baseline value extra-muscular disease activity MDAAT value, randomization stratification factors: disease diagnosis (DM vs. Non-DM), ILD, Region (Japan vs. ROW), time (categorical as study visit at which extra-muscular disease activity MDAAT is measured), time by baseline extra-muscular disease activity MDAAT and time by treatment interactions as fixed effects and subject as a random effect. Adjusted mean, SE, 95% CI for adjusted mean difference between treatment groups by study visit will also be provided.

A similar longitudinal model will also be used to assess the Myositis Response Criteria (MRC) total improvement score up to Day 169 (Week 24). The mixed model will include treatment group and randomization stratification factors: disease diagnosis (DM vs. Non-DM), ILD (absent vs. present), Region (Japan vs. ROW), time (categorical as study visit at which MRC is measured)

and time by treatment interactions as fixed effects and subject as a random effect. Adjusted mean, SE, 95% CI for adjusted mean difference between treatment groups by study visit will be provided.

Nominal p-values will be provided for the secondary efficacy endpoints at Day 169 i.e. mean change from baseline at Day 169 for each of the secondary endpoints: FI-2, HAQ-DI, extra-muscular disease activity MDAAT and MRC. The mixed longitudinal model will account for any missing values on any of the secondary efficacy endpoints.

The primary analyses of each of the secondary endpoints discussed above will be based on the data observed while subjects are on treatment in the study; a sensitivity analysis will be performed separately for each secondary endpoint that includes all the data collected at Week 24 on subjects who discontinue study medication prior to Week 24. Similar models as used for the primary analysis of these endpoints will be applied for the sensitivity analysis.

[REDACTED]

[Redacted]

[Redacted]

[Redacted]

[Redacted]

[Redacted]

[Redacted]

[Redacted]

[Redacted]

[Redacted]

[Redacted]

[Redacted]

[Redacted]

[Redacted]

[Redacted]

[Redacted]

[Redacted]

[Redacted]

[Redacted]

[Redacted]

Non-DM), ILD (absent vs. present), Region (Japan vs. ROW), time (categorical as study visits at

[REDACTED]

[REDACTED]

[REDACTED]

[REDACTED]

[REDACTED]

[REDACTED]

[REDACTED]

[REDACTED]

[REDACTED]

[REDACTED]

[REDACTED]

All AEs are coded and grouped into Preferred Terms (PT) by System Organ Class (SOC), using the most current version of the Medical Dictionary for Regulatory Activities (MedDRA), at the time of data base lock. Listings and summaries will be based on the resulting SOCs and PTs.

All reported AEs and SAEs will be listed, indicating the subject id, treatment group, age, gender, race, day of onset relative to start of dosing, resolution date, investigator-assessment of relationship to study drug, investigator-assessment of intensity of event, action taken regarding study drug and whether treatment was required for the event.

All adverse events with an outcome of death will be listed.

Any AEs that occur before the first injection of double-blind study drug or more than 56 days after the last injection during the double-blind period will be excluded from safety summaries in the Week 24 analysis. However, all reported AEs, including AEs that occurred more than 56 days post last dose for subjects who discontinued the study during the double-blind period or completed the double-blind period but chose not to enter the open-label period will appear in the above mentioned comprehensive listing.

Summary information (the number and percent of subjects) regarding AEs (for serious and non-serious events) will be tabulated by SOC, PT and treatment group for:

- Serious adverse events (SAE).
- SAEs related to study drug.
- AEs leading to study drug discontinuation.
- AEs related to study drug.
- AEs related to study medication categorized by intensity.
- Most common related AEs (reported in at least 2% of subjects in any treatment group).
- AEs by intensity.
- All AEs (serious or non-serious).
- Most common (serious or non-serious) AEs (reported in at least 5% of subjects in any treatment group).
- Laboratory AEs are laboratory results identified by the Investigator as AEs and thus reported on the AE pages of the CRF. Any such AE will be included in the respective AE summaries.

